12 QUALITY ASSURANCE AND CONTROL

12.1 Data Archiving

12.1.1 Forms

Data protection and confidentiality are guaranteed and no personal data is presented or published. The signed declaration of consent, as well as the completed questionnaire with the other personal data and demographic and medical personal data are stored in the original as a study document in a locked filing cabinet. Only the head of the study (head of the research laboratory of the University of Applied Sciences and Arts Southern Switzerland, Physiotherapy Graubünden) has access (key possession) to this cabinet. The encryption of the identity of the test persons is not digitally recorded, i.e. surname, first name and date of birth are not digitally recorded in any way.

Direct access to the personal data will continue to be allowed only to authorized persons of the CEC.

12.1.2 Specification of forms

The data collected in writing is recorded in the form listed in the enclosures and is marked as study data. They are therefore subject to data protection and are stored in accordance with the information described in chapter 12.1.1.

12.1.3 Archiving of data

The data collected will be kept for 10 years. Data protection will continue to be guaranteed.

12.2 Data management

12.2.1 Data Management System

The raw data of the perfusion of the skin microcirculation (Laser Speckle Contrast Imager) are processed with the software "moorFLPI-2 full-field laser Perfusion Imager V1.1". The oxygen saturation of the muscles and the brain is processed with the software "moor VMS-PC v.4.2.". The i-buttons are read out with the i-Button MMT software. The data from the thermal imaging camera is processed with the "Flir Research IR max" software. The oxygen saturation values of the muscles and the brain are also processed with the software "moor VMS-PC v.4.2.". Lactate and creatine kinase are recorded with the reflotron (Roche Diagnostic, Rotkreuz, Switzerland) and transferred to a data sheet. The balance measurement is recorded and evaluated with the Sway Star™ System (www.b2i.info). Sleep disorder, Lake Louis altitude sickness, dyspnea, state of mind and drowsiness are recorded in writing with a questionnaire. Cognition is recorded digitally on a laptop and the score is stored there. The subjective perceptual parameters regarding thermal comfort and temperature perception are asked orally and the answers are handwritten on the raw data sheet. The pain sensation is transferred to a portable PC on a supplied software (www.to-nod.com).

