
Measurements and procedures:
	
During the 20-minute acclimatization phase, the application areas are drawn (skin-friendly pen) and the appliances are attached. If necessary, the hypoxia mask is then put on, the treatment is started and the baseline measurements are carried out. After the baseline measurement, the 5-minute step-up task is performed. After this task, the physiological parameters are measured again. These measurements were followed by a 5-minute cold water bath of the hand. Afterwards, the physiological measurements are carried out up to 30 minutes after the cold water bath (5 min interval) and the questionnaires are filled out afterwards. In the terrestrial altitude situation, the test subject spends the night in the Hohsaas mountain restaurant (https://www.hohsaas-bergrestaurant.ch, canton of Valais) and the measurements are repeated the next day.
 
Perfusion of skin microcirculation
 
The perfusion of the skin microcirculation is visualized using the Laser Speckle Contrast Imager (moorFLPI 2, moor instruments, www.moor.co.uk). This measurement is measured during the baseline measurements, after the step-up task and up to 30 min after the cold water bath of the hand (5 min interval).
 
Oxygen saturation of the muscles and brain
 
The oxygen saturation of the muscles and brain is measured non-invasively with a deep tissue oxygenation monitor (moorVMS-NIRS, moor instruments, www.moor.co.uk). For this purpose, adhesive electrodes are attached over the muscle and forehead. This measurement is measured during the baseline measurements, after the step-up task and up to 30 min after the cold water bath of the hand (5 min interval).
 
Oxygen saturation of the blood
 
The oxygen saturation of the blood is measured with a portable pulse oximeter with finger clip probe (Nonin 7500, Nonin medical B.V., Plymouth, USA). This measurement is measured during the baseline measurements, after the step-up task and up to 30 min after the cold water bath of the hand (5 min interval).
 
Blood pressure and heart rate
 
The heart rate is measured with a heart rate belt and an additional 2-point ECG (Actiheart, Camntech Ltd., Cambridge, UK). Blood pressure is determined by means of an electronically automated upper arm blood pressure meter (Boso-Medicus uno). This measurement is measured during the baseline measurements, after the step-up task and up to 30 min after the cold water bath of the hand (5 min interval).
 
Skin temperature
 
Skin temperature is measured via the iButton system (www.ibuttonlink.com). The self-adhesive sensors transmit the information about the skin temperature wirelessly to a computer. Furthermore, the skin temperature is recorded by means of a thermal imaging camera (FLIR). This measurement is measured during the baseline measurements, after the step-up task and up to 30 min after the cold water bath of the hand (5 min interval).

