4.3 Secondary Objectives

The secondary goal is to compare and evaluate thermal comfort and temperature perception according to terrestrial altitude and simulated altitude. For this purpose, the following parameters are measured:

-

Subjective parameters:

- Thermal comfort
- Temperature sensation

SUPSI

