5.2 Secondary outcomes

Thermal comfort and temperature perception

This parameter is measured using a scale. The test subjects indicate their subjective temperature perception on a 9-point scale from -4 (very cold) to +4 (very hot). They then rate the thermal comfort between 0 (pleasant) and 4 (extremely unpleasant) on a 5-point scale. These measurements are carried out after the baseline measurement and after the cold water bath immersion of the hand.

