6.1.2 Blinding

Blinding the test subjects is not possible with regard to the situation.

It is not possible to blind the data collectors.

However, blinding the statistician can be guaranteed, who has no access to the personal data of the test persons and is not present during the data collection.

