8.4 Adherence to the study intervention

The test subjects are neither motivated nor unnecessarily distracted by the examiners or the study director with conversations. Communication is kept to a minimum, only study-related discussions are conducted in order not to influence the psychophysiological effects and to ensure homogeneity.

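### The two thermal ratings, the only secondary outcomes, are asked orally although data collectors cannot be blinded; a self-marked sheet would close an avoidable route for examiner influence

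*Combined protocol and SAP*

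**What the plan says.** On how the two thermal ratings are collected, section 12.2.1 (Data Management System) says: "The subjective perceptual parameters regarding thermal comfort and temperature perception are asked orally and the answers are handwritten on the raw data sheet". The same section treats the symptom and mood scales differently: "Sleep disorder, Lake Louis altitude sickness, dyspnea, state of mind and drowsiness are recorded in writing with a questionnaire". The synopsis (Measurements and procedures) adds that after the post-immersion measurements "the questionnaires are filled out afterwards".

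The two ratings carry the entire secondary objective. Section 4.3: "The secondary goal is to compare and evaluate thermal comfort and temperature perception according to terrestrial altitude and simulated altitude". Sections 5.2 and 9.1.3 define them as ratings that the participant gives on fixed scales: nine points from -4 to +4 for temperature perception, and five points from 0 to 4 for thermal comfort. Both are taken after baseline and after the cold-water immersion.

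On blinding, section 6.1.2 says of participants "Blinding the test subjects is not possible with regard to the situation" and of staff "It is not possible to blind the data collectors". Section 8.4 limits interaction during sessions: "Communication is kept to a minimum, only study-related discussions are conducted in order not to influence the psychophysiological effects".

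**The concern.** A rating spoken to someone who knows the condition can be affected by tone, by prompting, or by how an in-between reply is turned into a whole number. Neither participants nor data collectors can be blinded in this trial, so blinding cannot remove that influence. The way the rating is collected can.

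What is at stake is the comparison of simulated with terrestrial altitude on both secondary outcomes. If the examiner's influence were the same in the laboratory and in the hut, it would drop out of the comparison. If it differed, it would be read as a difference between the two kinds of altitude. Because these are the only two secondary outcomes and both are collected in this way, no other secondary outcome is free of the problem.

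**Working it through.** The plan contains no figure on this point. The sample-size calculation in 11.2 uses no input from the thermal ratings. The check is therefore mainly a comparison of sections, followed by algebra on the planned model.

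**1. What is stated and what is inferred**

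| Point | Source | Status |
|---|---|---|
| Thermal ratings asked orally, answers handwritten | 12.2.1 | Stated |
| Data collectors not blinded | 6.1.2 | Stated |
| Participants not blinded | 6.1.2 | Stated |
| Secondary objective consists of these two ratings only | 4.3, 5.2 | Stated |
| Symptom and mood scales on written questionnaires | 12.2.1 | Stated |
| Thermal ratings and questionnaires at the same time points | 5.1, 5.2, 9.1.2, 9.1.3 | Stated |
| A data collector asks and writes down the answer | 12.2.1 with 6.1.2 | Natural reading, not stated |
| Participants complete the questionnaires themselves | Synopsis, 12.2.1 | Natural reading, not stated |
| Fixed wording, or a rule for in-between answers | 5.2, 9.1.3 | Not given there; the data sheet (Appendix item 3) is not among the documents reviewed |

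**2. Could the influence differ between settings?** The documents give two reasons why it might.
- Simulated altitude is delivered through a mask (3.5, 8.2.1), and no section says that the mask comes off for the ratings. A spoken answer may therefore pass through a mask in the laboratory but not in the hut. Mask status at baseline is itself unclear: the synopsis puts the mask on before the baseline measurements, while 9.2.2 places baseline before exposure.
- Section 11.1 accepts that contact with other people in the hut can influence results. It also says that the hut's room temperature is matched to the laboratory only as far as possible, so staff may expect thermal answers to go in a particular direction.

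These are reasons why the influence could differ. They are not evidence that it does.

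**3. Where a shift would enter the planned analysis.** Section 11.4.2 plans situation (simulated, terrestrial) by time (baseline, post-immersion). Let the recorded mean be the true mean plus an examiner shift: m(S,t) + b(S) for simulated and m(T,t) + b(T) for terrestrial, each shift constant within its situation.
- Situation main effect: the bias is b(S) - b(T). It is zero only if the shifts are equal.
- Situation-by-time interaction: the bias is [b(S) - b(S)] - [b(T) - b(T)] = 0.

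A constant shift therefore reaches the main effect and cancels from the interaction. It would not cancel if it changed between baseline and post-immersion, for example if the mask were off at one and on at the other.

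**4. Illustration only.** The documents give no SD and no size of shift for these ratings. With two situation levels, and one terrestrial session compared with the simulated one, the main-effect test is equivalent to a paired t test on each participant's average over the two time points. Take N = 24, a two-sided level of 0.05, no true difference, and an assumed shift of d SDs of the paired difference. The noncentrality is d × √24, on 23 degrees of freedom.

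| Assumed d | d × √24 | Rejection probability |
|---|---|---|
| 0.1 | 0.49 | 7.6% |
| 0.2 | 0.98 | 15.6% |
| 0.3 | 1.47 | 29.1% |

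The values of d are arbitrary. The table shows what a shift would do if it existed. It says nothing about whether one exists, and it does not apply to the interaction.

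**The case against.** The case for leaving the procedure alone has real substance. The participant, not the examiner, gives the rating, and a one-digit answer on a bounded scale leaves little to interpret. The schedule in 9.1 lists the same ratings at the same points in all three situations. Section 8.4 allows talk that concerns the study, so asking a scheduled rating is permitted, and its limit on other conversation partly protects against prompting. The hypotheses in 11.1 are worded as change; if that means the situation-by-time interaction, a constant shift cancels. The measurement data sheet is an appendix that is not among the documents reviewed and may carry a printed scale or fixed wording. Participants know their situation, so their own expectations would remain on paper.

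All of this stands, and it limits the point to a risk. It does not remove the point. Section 12.2.1 still says that the ratings are asked orally. Section 8.4 limits conversation but does not set how a rating is to be asked. The planned model also has a situation main effect, where a constant shift does not cancel.

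A reader might infer three stronger things, and the documents support none of them:
- **That interviewer bias has been shown.** No section shows it.
- **That oral rating contradicts 8.4.** It does not, because study-related communication is allowed.
- **That the contrast with the written scales is itself a bias.** Each outcome is compared with itself across situations. The written questionnaires show only that a written route is workable at those time points.

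**Conclusion.** The point holds as a minor one. Both secondary outcomes are collected orally in a trial whose data collectors cannot be blinded, while written questionnaires are already in use at the same time points. This leaves an avoidable risk that examiner influence differs between laboratory and hut and shifts the situation main effect.

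The size of that risk is unknown and cannot be derived from the documents; the percentages in the illustration rest on assumed shifts and are not estimates. The conclusion assumes that the person asking is one of the unblinded data collectors and that the data sheet does not already have the participant mark the scale. It would be wrong to read it as saying that the secondary results are invalid or that a paper form would make them free of bias. The paper form removes the examiner's part and leaves the participant's expectation. This is a cheap improvement.

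**What to change.** In 5.2, 9.1.3 and 12.2.1, state that the participant marks temperature perception (-4 to +4) and thermal comfort (0 to 4) on a printed sheet that shows the scale labels. The sheet is handed over with the other written questionnaires, without spoken prompting, at both time points in all four sessions (simulated once, terrestrial twice, control once, per the table in 9.1).

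The cost is one extra form and its data entry: 2 scales × 2 time points × 4 sessions = 16 marks per participant, or 16 × 24 = 384 marks in all. These values already have to be transferred from the handwritten data sheet. No outcome, time point or analysis changes. If Appendix item 3 already contains such a sheet, only the wording of 12.2.1 needs to be brought into line with it.

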12.2.2 Data security and backup

The digital data (laser speckle contrast imager, i-button, thermal imaging camera, oxygen saturation, pain sensation, balance, cognition) will be anonymized and treated confidentially, access to the personal data will not be allowed to third parties. The digital data collected is stored solely on the institute's own computers and is not passed on to any external persons or transferred to other computers. Access to the computers of the research laboratory at the "University of Applied Sciences and Arts Southern Switzerland" is only granted to the head of studies and the examiners (listed in Chapter 1), as well as

SUPSI

persons authorised by the CEC.

12.2.3 Analysis and archiving

After collection, the digital data is encrypted and stored on another external hard drive for further backup. This is stored in a locked filing cabinet to ensure data protection.

12.2.4 Validation of electronic data

Immediately after data collection, the quality of the data is checked and verified with the help of the visual representation.

12.4 Audits and inspections

A report on the current status of the study is given orally to the study supervisor ([name]) on a monthly basis. In addition, [name] will be present during the measurements. This also includes demonstrating and presenting results and statistical analyses.

An annual report on the course of the study will be submitted to the CEC. Authorized persons of the CEC can view the data forms as well as the digital data on the institute's own computers at any time.

Data protection is guaranteed at all times.

12.5 Confidentiality and data protection

The examiners ensure that the privacy of the participant is guaranteed. In particular, data protection and confidentiality are guaranteed and no personal data is presented or published. The signed declaration of consent, as well as the completed questionnaire with the other personal details, are kept in the original as a study document in a locked filing cabinet.

The digital data will be anonymized and treated confidentially, and access to the personal data will not be allowed to third parties. The digital data collected is stored solely on the institute's own computers and is not passed on to any external persons or transferred to other computers.

Direct access to the personal data is only allowed to authorized persons of the CEC.

SUPSI

12.6 Retention of biological material and health-related data

-

SUPSI

13 PUBLICATION AND DISCLOSURE OF DATA

The examiners ensure that the privacy of the participant is maintained. In particular, the data protection and confidentiality of the data are guaranteed and no personal data is presented or published nor passed on to outsiders and unauthorized persons.

SUPSI

14 FUNDING AND SUPPORT

14.1 Financing

The study is funded by the University of Applied Sciences and Arts Southern Switzerland, Physiotherapy Graubünden. The auditors are employed by this institute and are remunerated for their work on this study in accordance with their employment contracts. No further support is needed.

SUPSI

15 INSURANCE

There is a public liability insurance policy with Basler Versicherung for Thim van der Laan AG in Landquart, where the study is being conducted.

SUPSI

17 APPENDIX

1. Subject information, informed consent and demographic data (health questionnaire)
2. Recruitment of test persons (advertisements)
3. Data Collection Questionnaire Measurements (Screening Test and Measurement Data Sheet)
4. Protocol Synopsis
5. Employee
6. CVs of all examiners
